Study protocol:
Impact of Repeated Antioxidant
Supplementation of Embryo Culture Media on
Blastocyst Utilization and Expansion Rate Under
Two Different O₂
Concentrations

October 31st, 2021

Title: The Role of Antioxidants in Mitigating Reactive Oxygen Species and Oxidative Stress in Assisted Reproduction Techniques: A Comparative Study

Introduction:

During assisted reproduction techniques (ARTs), monitoring the laboratory environment is essential for adequate embryo development and any deviation from optimal conditions could increase reactive oxygen species (ROS) (Kaskar, 2021). Excessive ROS is detrimental to early embryo development (Kaskar, 2021). Reactive oxygen species constitute highly reactive chemicals associated with oxidative stress (OS) and subsequent cellular damage to gametes and embryos (Lane & Lyons, 2000; Swain, 2010). Oxidative stress is observed when the accumulation of ROS molecules exceeds the capacity of antioxidants (AOXs) defense mechanisms to neutralize them, subsequently promoting lipid, protein, as well as DNA damage (Lane & Lyons, 2000; Swain, 2010).

In the past, embryo culture was performed in atmospheric O₂ concentrations of about 20% (Nastri et al., 2016). However, an O₂ concentration of 5% was found superior in terms of enhancing clinical pregnancy rate, live births, as well as implantation rate (Kaskar, 2021). Several exogenous factors affecting embryo development during in vitro culture, namely the type of infertility, as well as advanced maternal and paternal age, have been correlated with high levels of ROS production in gametes and embryos, which in turn result in decreased fertilization, implantation, and live birth rates, and increasing aneuploidy rates (Lane & Lyons, 2000; Edwards et al., 1998; Hong et al., 2014; Chui et al., 2008)

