- Group 1A: Antioxidants will be administered every 12 hours at 5% O₂ tension.
- Group 1B: Antioxidants will be administered every 12 hours at 20% O₂ tension.
- Group 2A: Antioxidants will be administered once at the beginning of embryo culture at 5% O₂ tension.
- Group 2B: Antioxidants will be administered once at the beginning of embryo culture at 5% O₂ tension.

Methods:

Study Location and Duration:

The study will be conducted at the Center for Technological Innovation and Reproductive Medicine (CITMER), Mexico City, Mexico, from October 2021 to May 2022.

Participants:

Eligible participants will include infertile women with tubal factor, polycystic ovary syndrome, uterine factor, and unexplained infertility, who have had fertilization of more than 2 oocytes by conventional in vitro fertilization (cIVF) and intracytoplasmic sperm injection (ICSI).

Exclusion criteria will involve low ovarian response patients (fewer than 6 oocytes obtained after oocyte retrieval) and patients older than 37 years.

Sample Size and Group Allocation:

A total of 3603 zygotes obtained from 293 patients will be included in the study.

The zygotes will be divided into four groups based on the following conditions:

Group 1A: Antioxidants will be administered every 12 hours at 20% O₂ tension (793 zygotes).

Group 1B: Antioxidants will be administered only at the beginning of embryo culture at 20% O₂ tension (1286 zygotes).

Group 2A: Antioxidants will be administered every 12 hours at 5% O₂ tension (695 zygotes).

Group 2B: Antioxidants will be administered only at the beginning of embryo culture at (829 zygotes).

The procedures followed for IVF/ICSI involved the following steps:**Ovarian stimulation:**

Different ovarian stimulation protocols were used, including the gonadotropin-releasing hormone (GnRH) antagonist protocol with Cetrotide®, in combination with rFSH and rLH in Pergoveris®.

GnRH antagonist protocols were also used with follitropin alfa in Gonal-F® or with human menopausal gonadotropin in Merapur®

Gamete Retrieval:

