Timeline and Frequency of Assessments:

Data collection will be performed at specific time points, specifically on day 5 and day 6 of the study.

Outcome Measures:

- Usable blastocysts on day 5.
- Expanded blastocysts on day 5.
- Usable blastocysts on day 6.
- Expanded blastocysts on day 6.
- Cumulative usable blastocysts.
- Cumulative expanded blastocysts.

Ethical Considerations:

The study was conducted in accordance with the Declaration of Helsinki and approved by the Institutional Ethics Committee of CITMER CE-20-102.

Data analysis

The statistical analysis of the data will be performed using the R statistical software by the R Core Team.

Statistical Methods:

For statistical analysis, the data collected consisted of the continuous variable of age, which was expressed as the mean \pm standard deviation in each study group. In addition, the frequency and percentage of usable and expanded blastocysts were recorded as categorical variables.

Comparisons between usable and expanded blastocysts from each treatment were performed by calculating the odds ratio and chi-square test. A significance level of $p < 0.05$ was established to determine the existence of statistically significant differences between groups.

References.

1. Khalied Kaskar, C. Optimizing embryo culture conditions and spent culture media analysis as predictors of embryo quality and pregnancy; PhD Thesis, University of the West Cape, Cape Town, South Africa, February 2021.
2. Swain, J.E. Optimizing the culture Environment in the IVF Laboratory: Impact of PH and Buffer Capacity on Gamete and Embryo Quality. *Reprod Biomed Online* **2010**, *21*, 6–16.
4. Nastri, C.O.; Nóbrega, B.N.; Teixeira, D.M.; Amorim, J.; Diniz, L.M.M.; Barbosa, M.W.P.; Giorgi, V.S.I.; Pileggi, V.N.; Martins, W.P. Low versus Atmospheric Oxygen Tension for Embryo Culture in

Assisted Reproduction: A Systematic Review and Meta-Analysis. *Fertil Steril* **2016**, *106*, 95-104.e17, doi:10.1016/j.fertnstert.2016.02.037.

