Statistical analysis plan:

Impact of Repeated Antioxidant Supplementation of Embryo Culture Media on Blastocyst Utilization and Expansion Rate Under Two Different O₂ Concentrations

October 31st, 2021

Research Questions:

- What is the effect of antioxidant supplementation and O2 tension on blastocyst utilization rate and blastocyst expansion rate in infertile women?
- Are there any significant differences in the outcomes between the different antioxidant supplementation protocols and O2 tensions?

Statistical Tests:**Sample Size:**

The total number of blastocysts analyzed was 1797, obtained from 3603 zygotes and 4924 inseminated oocytes. The study included 293 infertile women with a mean age of 32.2 ± 3.3 years.

Data Handling:

For statistical analysis, the data collected consisted of the continuous variable of age, which was expressed as the mean \pm standard deviation in each study group. In addition, the frequency and percentage of usable and expanded blastocysts were recorded as categorical variables.

Comparisons between treatments were performed by calculating the odds ratio and the chi-square test. A significance level of $p < 0.05$ was established to determine the existence of statistically significant differences between groups.

Confounding Variables:

Other treatments or medications: Although there is no explicit mention of other treatments or medications received by the participants in addition to antioxidant supplementation, it is essential to acknowledge that there may be confounding variables present. It is possible that other interventions or medications used in the management of infertility could interact with antioxidant supplementation and potentially influence the study outcomes.

Sensitivity analysis:

The odds ratio analysis with a confidence interval of 95%

9. Statistical Software:

R Core Team was employed for statistical analysis.

10. Data Interpretation:

The results were interpreted by analyzing and comparing the blastocyst utilization rates, blastocyst expansion rates, and cumulative blastocyst utilization and expansion rates across the four study

groups. Statistical analyses, such as odds ratios (OR) and chi-square tests, were used to determine the significance of the differences observed. The level of significance was set at $p < 0.05$.

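### Maternal age and type of infertility, which the protocol itself names as prognostic, enter no comparison, and the SAP's remark on unmentioned treatments is contradicted by the protocol

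*Protocol*

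**What the plan says.** **Use of age.** Protocol, Statistical Methods, and SAP, Data Handling, describe age in the same way: "the data collected consisted of the continuous variable of age", given as a mean and SD in each study group. It appears in no test or model. The SAP gives one overall figure: "The study included 293 infertile women with a mean age of 32.2 ± 3.3 years".

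**Comparisons.** Both documents plan an odds ratio and a chi-square test, without covariates or strata. The SAP's sensitivity analysis is a 95% interval on that odds ratio. Its subgroups are the two treatment factors, oxygen tension and supplementation schedule.

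**Prognosis.** The protocol's Introduction lists type of infertility among the factors affecting embryo development, and adds that "advanced maternal and paternal age, have been correlated with high levels of ROS production", with lower fertilisation, implantation and live birth rates as the consequence.

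**Other treatments.** SAP, Confounding Variables, says "there is no explicit mention of other treatments or medications received by the participants" beyond the antioxidants. It grants that other infertility treatments might influence outcomes, but attaches no method to that. Protocol, Ovarian stimulation, says "Different ovarian stimulation protocols were used" and names the products. Gamete Retrieval names the trigger agent, and Participants and Fertilization describe both conventional IVF and ICSI.

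**The concern.** The protocol ties maternal age to reactive oxygen species, the mechanism that the intervention targets, and the trial holds each woman's age. A crude two-by-two comparison cannot use it. If older women, or women with a less favourable diagnosis, contributed more zygotes to one group, the odds ratio would carry that difference as if it were a treatment effect, and nothing planned would reveal or remove it.

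Randomisation normally limits this worry. Here the reassurance is incomplete. Protocol, Allocation, says that zygotes are randomly assigned but gives no ratio, blocking or stratification, and does not say whether a woman's zygotes go to one group or are spread over several. The group sizes are far from equal.

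The SAP sentence on other treatments is a separate fault. It does not cause the lack of adjustment, which follows from the choice of tests. It does mean that the only paragraph on confounding starts from a premise that the protocol contradicts.

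**Working it through.** **Inputs from the documents.** Group sizes of 793, 1286, 695 and 829 (Protocol, Sample Size and Group Allocation); 293 women; age SD 3.3 years across women (SAP, Sample Size); 1797 blastocysts from 3603 zygotes. Groups 1A and 2A are taken as the 12-hourly groups, as in that protocol section, in Antioxidant Supplementation and in the SAP. The list under Allocation labels the groups differently.

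**Assumptions.** The usable-blastocyst rate changes by 1 to 2 percentage points per year of age (the documents give no figure); the outcome rate is near 50%; the SD of 3.3 also applies across zygotes; women contribute similar numbers of zygotes.

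**1. The plan's own figures.** 793 + 1286 + 695 + 829 = 3603, as stated. 1797/3603 = 49.9% blastocysts per zygote. 3603/293 = 12.3 zygotes per woman.

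**2. Evenness of the groups.** Shares are 22.0%, 35.7%, 19.3% and 23.0%. Against an assumed equal split of independent zygotes, chi-square = 230.4 on 3 df. The documents state no ratio, so this shows only that simple equal allocation of single zygotes does not describe these groups.

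**3. Pooled schedule contrast.** Every 12 hours: 793 + 695 = 1488 zygotes. Once only: 1286 + 829 = 2115.

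- Naive SE of the difference in rates = √(0.25 × (1/1488 + 1/2115)) = 0.0169, or 1.7 points.

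**4. Chance age imbalance, zygotes randomised individually.**

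- SE of the difference in mean age = 3.3 × √(1/1488 + 1/2115) = 0.11 years.
- 95% limit = 1.96 × 0.112 = 0.22 years.
- Shift at 1 to 2 points per year = 0.2 to 0.4 points.

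**5. Chance age imbalance, whole women allocated.**

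- Women pro rata: 293 × 1488/3603 = 121 and 293 × 2115/3603 = 172.
- SE = 3.3 × √(1/121 + 1/172) = 0.39 years.
- 95% limit = 1.96 × 0.39 = 0.77 years.
- Shift = 0.8 to 1.5 points.

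**6. Like for like.** Steps 4 and 5 give 95% limits; the 1.7 points is one SE. On the SE scale, whole-woman allocation adds 0.39 to 0.78 points: √(1.69² + 0.39²) = 1.73 and √(1.69² + 0.78²) = 1.86, an inflation of about 3% to 10%.

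**7. Effect of adjustment on precision.** Near 50%, 1 to 2 points per year is a log odds ratio of 0.04 to 0.08 per year.

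- Crude SE of the schedule log odds ratio = √((1/0.25) × (1/1488 + 1/2115)) = 0.0677.
- With age in the model, the average of p(1 − p) is about 0.25 − (0.04 × 3.3)²/16 = 0.2489, or 0.25 − (0.08 × 3.3)²/16 = 0.2456.
- The SE becomes 0.0677 × √(0.25/0.2489) = 0.0678, or 0.0677 × √(0.25/0.2456) = 0.0683.

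Adjustment therefore raises this SE slightly.

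No adjusted odds ratio can be computed, because the documents give no age, diagnosis, regimen or insemination counts by group.

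**The case against.** The strongest reply is that zygotes are randomised. A crude comparison is then unbiased in expectation, and step 4 shows that chance age imbalance would be trivial. If each woman's zygotes were deliberately divided among the groups, age would be balanced within woman. Even under whole-woman allocation, variation between women is largely a clustering matter, and a standard error clustered by woman already counts it. The Introduction also speaks of advanced age, while the trial excludes women over 37. All of this stands and limits the size of the point. It does not remove it, because the documents do not say which allocation was used and the group sizes do not settle it.

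Several stronger readings are tempting and are not supported:

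- **Uneven groups prove that randomisation failed or that the groups differ in age.** No ratio is stated, and no ages by group are given.
- **The effective sample for balance is 293 women.** This is so only if whole women were allocated, whereas the protocol speaks of zygotes.
- **Adjustment would tighten the estimate.** For a logistic odds ratio it need not, as step 7 shows.
- **Insemination method and stimulation regimen are established prognostic factors.** The documents do not say so of conventional IVF versus ICSI, and the SAP calls other infertility treatments only a possible influence. Type of infertility has better support.

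**Conclusion.** The point holds in a limited form. Age is collected and only summarised, no comparison uses age or type of infertility, and the protocol names both as affecting embryo development. The SAP's statement on other treatments conflicts with the protocol.

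The size depends on an allocation method that the documents leave open. For the pooled schedule contrast, the 95% limit of the shift from age is about 0.2 to 0.4 points with individually randomised zygotes and about 0.8 to 1.5 points with whole women, beside a naive SE of 1.7 points. Both ranges rest on the assumed 1 to 2 points per year and cover chance imbalance in age alone. They put no bound on imbalance from non-random assignment, or on imbalance in diagnosis. A reader might infer that the reported benefit of repeated supplementation is an age artefact; nothing in the documents shows that. What they support is that balance has not been shown and that the planned analysis could not correct for its absence.

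**What to change.** 1. Tabulate age, type of infertility, stimulation regimen and insemination method by group, and state whether a woman's zygotes were kept together or divided.
2. For each outcome, fit a logistic model clustered by woman, with age (continuous) and type of infertility as covariates. Add stimulation regimen and insemination method where recorded.
3. Report the adjusted estimate beside the crude one. Fix the covariate list before running the model and label the analysis post hoc, because the SAP already reports results.
4. State that crude and adjusted odds ratios can differ through non-collapsibility even when groups are balanced. An adjusted risk difference avoids this.
5. Replace the SAP sentence on unmentioned treatments with the regimens that the protocol lists.

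**Cost.** Slightly more analysis work, a revised SAP paragraph, and possibly a slightly larger SE for the log odds ratio. Age is already held and type of infertility is an eligibility criterion. Availability of regimen and insemination records is assumed.

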Therefore, it is conceivable that even minimal handling of gamete and embryos could induce OS. This assumption highlights the demand for strategies aiming to reduce the detrimental effects of OS. Implementation of AOX supplementation could help protect against OS damage attributed to alterations in laboratory conditions in the IVF setup. Antioxidants act as a counterpart of ROS, inhibiting their overproduction or neutralizing them when provided in sufficient concentrations (Agarwal et al., 2005; Carocho & Ferreira, 2013). The role of AOXs in enhancing the embryo's potential to successfully reach the blastocyst stage has been demonstrated (Guerin, 2001; Budani & Tiboni, 2020). The blastocyst quality of the expansion grade has been analyzed by the measurement of the blastocoel and has been associated with increased ongoing pregnancy rates (David Gardner et al., 1999)

Considering the pivotal role of AOXs *in vivo*, their implementation in embryo cultures *in vitro* is thought to help mimic the human reproductive tract's natural conditions. Previous studies have investigated the role of non-enzymatic AOX molecules namely vitamin C, vitamin E, selenium, zinc, taurine, hypotaurine, glutathione, and carotene on embryo culture (Agarwal et al., 2005; Carocho & Ferreira, 2013).

Previously, our group determined the oxidation-reduction potential (ORP) values of follicular fluid in oocyte donors and established them as the "physiological" desirable ORP in embryo culture media to maintain a redox state during the entire embryo culture similar to what is observed *in vivo* (Truong, T., & Gardner, D.K., 2017)

However, the current literature is lacking studies to develop a physiological *in vitro* AOXs system that can effectively mitigate the OS phenomenon.

The present study aims to explore whether repeated supplementation of the embryo culture medium with AOXs every 12 hours to culture embryos in ORP physiological levels, could improve the cumulative rates of usable and expanded blastocysts of human embryos from infertile patients as assessed at two different O₂ concentrations (5% and 20% O₂) on days 5 and 6.

Research Design:

Study type: Interventional

Study Model: Parallel Assignment

Participants: 293 Infertile women aged 18 to 37 years at the time of oocyte collection, with tubal factor, polycystic ovary syndrome, uterine factor, or unexplained infertility.

Allocation

Zygotes will be randomly assigned to one of four groups.

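### The only planned tests treat sibling embryos as independent, and the sibling-allocation rule that decides whether this is safe is not given

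*Protocol*

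**What the plan says.** The Protocol, under Statistical Methods, states: "Comparisons between usable and expanded blastocysts from each treatment were performed by calculating the odds ratio and chi-square test". The SAP, under Data Handling, repeats it: "Comparisons between treatments were performed by calculating the odds ratio and the chi-square test". Both set significance at p < 0.05. The SAP's Sensitivity analysis consists of "The odds ratio analysis with a confidence interval of 95" per cent, which is the same estimate with its interval. The SAP's section on confounding acknowledges other treatments but plans no adjustment. No mixed model, GEE, cluster-robust, stratified or paired analysis appears in either document.

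On the data, the Protocol's Sample Size and Group Allocation section says: "A total of 3603 zygotes obtained from 293 patients will be included in the study". The SAP's Sample Size section says: "The total number of blastocysts analyzed was 1797, obtained from 3603 zygotes and 4924 inseminated oocytes".

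On allocation, the Protocol says first "Zygotes will be randomly assigned to one of four groups" and later "The zygotes will be divided into four groups based on the following conditions". Neither statement gives a ratio, a stratification, or a rule for zygotes from the same woman.

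The SAP's second research question is "Are there any significant differences in the outcomes between the different antioxidant supplementation protocols and O2 tensions", so O2 comparisons are in scope as well as supplementation comparisons.

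**The concern.** Embryos from one woman share her age, diagnosis, stimulation and gametes, so their outcomes are likely to be correlated. A chi-square test on embryos assumes independence. How much that matters depends on how siblings are allocated:

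1. **Each zygote randomised independently.** The test holds its level approximately.
2. **Siblings split evenly over the groups.** The test is somewhat conservative.
3. **Whole cohorts sent to one group.** Every comparison is anti-conservative and every confidence interval too narrow.
4. **O2 set by woman, siblings split on supplementation.** Supplementation comparisons within one O2 level are safe. O2 comparisons and any four-group test are inflated.

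These cases are not exhaustive, and the documents do not say which applies. Case 4 is plausible because the Protocol has the incubator control O2, but nothing states or excludes it. Both documents summarise age, a woman-level variable, by study group. That is compatible with women belonging to groups but does not prove it.

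The SAP's Data Interpretation section already draws practical conclusions from these tests. Its sensitivity analysis could not reveal the problem, because it makes the same independence assumption.

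**Working it through.** **Inputs from the documents.** 293 women, 3603 zygotes, 1797 blastocysts; group sizes 793, 1286, 695 and 829; alpha 0.05, taken as two-sided.

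**Inputs assumed.** ICC 0.02, 0.05, 0.10 and 0.20; outcome proportion 0.5; equal cluster sizes unless stated. The documents give no ICC and no power calculation.

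**Reproducing the plan's figure.** 793 + 1286 + 695 + 829 = 3603, as stated. With ICC 0, the simulated chi-square rejects 4.2% to 6.2% of the time (3000 runs, Monte Carlo SE about 0.4 points), so it is sound when embryos really are independent.

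**Cluster size.** 3603/293 = 12.30 zygotes per woman; 1797/293 = 6.13 blastocysts per woman. The Protocol defines expansion as a proportion of blastocysts. No denominator is stated for usable blastocysts, so both are shown.

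**Group totals.** Equal allocation expects 3603/4 = 900.75 per group. The sum of (observed − 900.75)²/900.75 is 230.4 on 3 df, p about 1e-49. Equal-probability randomisation of each zygote does not fit. Since no ratio is stated, this does not identify the unit.

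**Case 3, formula.** Design effect DE = 1 + (m − 1) × ICC; true error = 2 × (1 − Φ(1.96/√DE)); the correct interval is √DE times wider.

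| ICC | 0.02 | 0.05 | 0.10 | 0.20 |
|---|---|---|---|---|
| Zygotes, DE | 1.23 | 1.56 | 2.13 | 3.26 |
| Zygotes, true error | 7.7% | 11.7% | 17.9% | 27.8% |
| Zygotes, interval width factor | 1.11 | 1.25 | 1.46 | 1.81 |
| Blastocysts, DE | 1.10 | 1.26 | 1.51 | 2.03 |
| Blastocysts, true error | 6.2% | 8.0% | 11.1% | 16.9% |
| Blastocysts, interval width factor | 1.05 | 1.12 | 1.23 | 1.42 |

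**Case 2, formula.** DE = 1 − ICC gives 4.8%, 4.4%, 3.9% and 2.8%.

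**Simulation.** Beta-binomial outcomes under the null, 293 women, group probabilities 0.220/0.357/0.193/0.230 (equal shares for even splits), 12,000 runs per cell (Monte Carlo SE 0.2 points at 5%). Groups are coded as in the Protocol's Sample Size and Group Allocation list. Entries are the type I error of the planned chi-square at ICC 0.02/0.05/0.10/0.20.

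| Comparison | Zygotes, % | Blastocysts, % |
|---|---|---|
| Case 3, 1A vs 1B | 8.0/12.0/18.4/27.4 | 6.2/7.6/11.1/17.2 |
| Case 4, O2 at 12-hourly level | 5.8/7.8/10.9/15.7 | 5.3/6.5/7.7/10.1 |
| Case 4, O2 at once-only level | 6.5/9.3/12.6/19.5 | 5.7/6.7/8.6/12.1 |
| Case 4, O2 pooled over supplementation | 7.7/12.1/17.8/27.9 | 6.3/8.1/11.0/17.0 |
| Case 4, four-group test | 6.2/9.2/13.2/20.6 | 5.6/6.6/8.7/12.5 |

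Case 1 gives 4.6% to 5.6% throughout. In case 4, supplementation within one O2 level gives 4.8% to 5.3% if siblings are split independently and 2.7% to 5.1% if split evenly.

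**Unequal cluster sizes** (coefficient of variation 0.5, 4000 runs) raise case 3, 1A vs 1B, to 8.9/14.1/21.0/32.0% with zygotes and 6.7/8.9/13.1/19.6% with blastocysts.

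**Clustered alternative.** A logistic GEE with independence working correlation and a sandwich variance by woman gives 4.6% to 6.0% over all cases, both denominators and all ICCs, and 4.5% to 6.5% with unequal cluster sizes.

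**The case against.** The strongest reply is that the Protocol says zygotes are randomised. Read literally, that is case 1: the planned test holds about 5% and the GEE improves nothing on type I error. Cases 3 and 4 are constructions that no section states. Even in case 4, the contrast that the SAP's interpretation emphasises, 12-hourly against once-only, is not inflated within an O2 level. This stands, and it is why the plan cannot be called anti-conservative outright. It does not remove the point, because the validity of every test then rests on one unelaborated sentence.

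The inflation sizes depend on an assumed ICC and an assumed outcome proportion. That also stands. The direction under each allocation rule does not depend on the ICC value. If day-5 or day-6 expansion uses only that day's blastocysts, clusters are smaller than 6.1 and inflation is lower.

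The group totals carry little weight: independent randomisation at unequal probabilities would also hold 5%.

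On the remedy, three limits are fair. The claim that a GEE targets the crude odds ratio is secure with independence working correlation, so that must be specified. The simulation has the woman as the only source of correlation; the Protocol pairs 20% O2 with 95% humidity and 5% O2 with 25%, and clustering by woman cannot separate those. The random-intercept model suggested below as a sensitivity analysis was not simulated.

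**Conclusion.** The concern holds as an omission with conditional consequences. It is certain that the plan's only tests ignore the woman and that the sibling rule is missing. Under the closest reading of the Protocol the tests keep about 5%. Over the ICCs assumed, with equal cluster sizes, whole-cohort allocation would put the two-group error at about 8% to 28% with zygotes and 6% to 17% with blastocysts. O2 set by woman would put the O2 comparison at one supplementation level at about 6% to 20% with zygotes and 5% to 12% with blastocysts.

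The documents do not show which case applies. The SAP's interpretation reports only the direction of effects, so they also do not show that any reported result would change. The clustered analysis stays close to 5% in all four cases and the planned test does not, which is reason enough to change it.

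**What to change.** - Replace the crude odds ratio and chi-square with a logistic GEE, independence working correlation, robust standard errors clustered by woman. Report its marginal odds ratio with a cluster-corrected 95% interval for all six outcomes.
- State the unit of allocation, the rule for siblings, the allocation ratio and the denominator of each outcome.
- Reconcile the Protocol's two group lists before coding the groups. They attach different supplementation and O2 conditions to the same labels, and the later list gives no O2 level for group 2B.
- Replace the present sensitivity analysis with a random-intercept logistic model, labelled as a conditional odds ratio because its target differs from that of the GEE.

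The cost is a reanalysis of existing data, since the SAP already reports findings, and some SAP wording. It needs a woman identifier linked to each embryo, which is assumed to exist. Intervals may widen and some p-values may become less favourable. With 293 women the GEE Wald test can run slightly above nominal, up to 6.0% with equal and 6.5% with unequal cluster sizes in the simulation.
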